5.4 Prior and Concomitant Therapy

All current therapies and medications will be allowed to continue throughout the study, except those listed in the exclusionary criteria section.

Parents will be educated that megestrol is a steroid, and what to do if their child becomes acutely ill and the treating provider prescribes a steroid. So, if the child is prescribed a steroid (oral or inhaled), the parents should consult with the treating physician to see if a non-steroidal option is available. If not, and the treating physician proceeds with steroids for medical reasons, the parent should contact the iKanEat study team to inform them of this prescription.

If the prescription is over 7 days, then the iKanEat medical monitor will review the case and decide how to proceed with the study drug. Options could include tapering off the study drug temporarily and to reactivate after the prescription is given; or, tapering early if the child is in the final weeks of study drug; or other options as deemed appropriate by the medical monitor.

If the prescription is 7 days or less, than the study team will note it in the REDCap Case Report Form and report it to the medical monitor, but no action will be taken.

5.5 Packaging

The drug will be placed in bottles and will be dispensed directly or from the investigational pharmacy.

5.6 Blinding of Study Drug

The drug will be dispensed by the investigational pharmacy at each site, who will be the only unblinded part of the team. They will receive the random codes prepared by the study statistician, and will dispense placebo/megestrol as appropriate.

5.6.1 Storage

The drug will be stored at room temperature in amber bottles.

5.6.2 Dispensing of Study Drug

The megestrol/placebo will be dispensed by each site's investigational pharmacy. Site pharmacists may round doses to the nearest 0.1 ml if not done previously by the investigator. Refer to the pharmacy manual for detailed instructions and a dosing table.

CONFIDENTIAL

This material is strictly confidential and is intended solely for the guidance of clinical investigation. Do not disclose or use except as authorized in writing by the study sponsor

Regular study drug reconciliation will be performed to document drug assigned, drug consumed, and drug remaining. This reconciliation will be logged on the drug reconciliation form and signed and dated by a member of the study team.

6 Study Procedures

iKanEat Intervention

The 24 week iKanEat intervention is composed of 4 clinic visits and a series of approximately 14 (See Table 3. Procedures Timeline). Serious Adverse Events (SAEs) will be assessed at every point of contact.

Clinic Visits

Clinic visits will occur at each site (see Sites) in their clinical space. Each visit will involve obtaining weight and height (in triplicate, in light clothing), vital signs, and then speaking with a healthcare practitioner regarding overall health. The child will also receive a complete physical exam, similar to a routine pediatric visit, including blood pressure and temperature, and will also be assessed for side effects of the iKanEat protocol. All participants will complete a blood draw at weeks 10 and 14. Participants taking inhaled or intranasal steroids will take an additional blood draw at week 0. At the initial clinic visit a medical history will also be obtained.

Remote Clinical Visits

In the event clinics are closed (ie. COVID-19 outbreak) or when convenient for patients, clinical visits will be conducted remotely via the Zoom teleconferencing app. Any supplies needed (stool collection kits, scale, tape measures, iPad with data, etc.) will be mailed to the family in advance. If parents do not have a device compatible with the Zoom app, they will be loaned a device with a data plan. Parents will be trained on how to obtain height and weight at home. Digital scales and tape measures will be sent to the families (or they may use their own if they have them), and each family will measure the height and weight during a video call via Zoom app with an iKanEat team member to ensure measurement accuracy. Other vitals, such as blood pressure, pulse, and temperature will not be obtained remotely. Participants will be asked to collect a stool sample and store it in their home freezer until the sample can be obtained by iKanEat study personnel via FedEx shipping or drop-off at the local site.

Tele-Visits

Tele-visits will begin by building rapport and asking for a summary of all relevant information since the last point of contact, including parent perception of changes in weight, feeding habits, progress, stress of parent/child, and illness. Children will be assessed for side effects of the iKanEat protocol at every tele-visit per parent report. The majority of the time left in the 30 minute session will be spent dealing with parent concerns, which our previous project indicates may include questions about measures, questions about implementation of the iKanEat protocol, and ensuring that children/families adhere to the oral-motor and behavioral guidelines for feeding (see Table 1 and 2). Specifically, we will assess for the presence of daily mealtimes (at least 3-5 times per day), limited grazing between planned meals/snacks, consistent mealtime location, appropriate meal length (approx. 20 minutes), and limited distractions during mealtime (refrain from use of TV, iPad, toys, etc.). Families will also be encouraged to engage in family mealtime together, to prohibit force feeding across all feeders, and to focus on positive parent behavior, positive meal demeanor, and appropriate food presentation (as defined in Table 2). Motivational interviewing and cognitive behavioral parent training techniques will be used to improve parent performance on these skill areas. These skills will rely heavily on the detailed training manuals available from The Incredible Years, and our therapists will specifically use the materials from the book "Collaborating with Parents to Reduce

CONFIDENTIAL

This material is strictly confidential and is intended solely for the guidance of clinical investigation. Do not disclose or use except as authorized in writing by the study sponsor

Children's Behavior Problems: A book for Therapists Using the Incredible Years Programs." The structure and content of these tele-visits is based directly on those used in our prior work (HD066629). All visits (clinic and tele-visits) will focus directly on the oral-motor and behavioral skills necessary for oral eating.

Tele technology

Parents will be allowed to choose if they wish to receive their tele-visits over phone (as we did in our previous work) or via interactive televideo (such as Skype or Facetime). For patients who choose to do the visits over phone, we will provide a toll free number with a fully secure connection. For patients who choose to use the tele-visit option, KUMC also has access to the Zoom Mobile Meeting Platform which provides a secure videoconference bridge. These point-to-point connections are highly secure, meaning there is no concern about the release of protected health information. The Zoom platform also allows for the connection of diverse types of systems, including mobile devices, desktop computers, and established telehealth equipment in many clinical settings (important for eventual dissemination, if appropriate). The Zoom app or a similar secure technology will be utilized to connect participants to the researchers for all study procedures. No matter whether patients chose to receive their tele-visits over phone or interactive televideo, they will be using their own existing device, such as a home phone, cell phone, desktop computer or tablet device, a study-owned device that is loaned to the participant. Tele-visits will be recorded to ensure interventionist adhere to the treatment manual and for patient care purposes.

Interventionists

Interventionists for the clinic visits will be pediatric healthcare providers accompanied by study team staff at each site (see letters of support). These providers are experts in feeding and serve as the physicians and/or Medical Directors of the feeding programs at their sites (see letters of support). Interventionists for the tele-visits will be behavioral experts at the University of Kansas Medical Center and are trained multidisciplinary feeding team members with telehealth experience, including two PhD level psychologists ([name], [name]), and a research dietitian who worked with the team as an interventionist on the previous study. All behavioral interventionists are trained in motivational interviewing and in cognitive behavioral parent training and are familiar with The Incredible Years program that will serve as a basis for the behavioral parent training program used here.

Fidelity

Treatment fidelity for tele-visits will be measured by having a Graduate Research Assistant code a randomly selected sample of 10% of all intervention sessions (via video recording). They will code for adherence to the visit checklist. The recordings will be selected and coded via a random numbers table.

6.1 Pre-Screening Session (-14 to -1 day before Week 0)

Participants will be identified through ongoing multidisciplinary feeding teams at the participating sites. Pre-screening sessions will occur within a regularly scheduled clinical care visit. The study team will evaluate the patient for eligibility, and families will be invited to participate and consent forms signed.

If approved, electronic consent will occur in person during a regularly scheduled clinic visit. A member of the study team will pull up the consent document on tablet and review the form with the participant. The participant and study personnel will sign the document by finger or stylus. After the consent form is submitted, the study personnel will receive a prompt in REDCap to print a pdf copy of the signed consent and give to the participant during the visit. The study personnel will also have the option to email a copy of the consent to the participant directly from REDCap. As this is a multi-site study, the e-consent process will be done in accordance with state laws of the participating site.

CONFIDENTIAL

This material is strictly confidential and is intended solely for the guidance of clinical investigation. Do not disclose or use except as authorized in writing by the study sponsor

If the consenting visit is conducted remotely, the study team will have the option of doing the e-consent over a tele-video call (Zoom). In this case, the REDCap e-Consent template will be modified so that the parent can open the parent signature e-Consent page on their device during the Zoom call. After the consent discussion, the parent will sign their REDCap signature form and submit. The study personnel will sign the study personnel signature form on their device and save. The participant will be provided with a copy of the consent form as well as the signature pages of both the parent and study personnel.

Alternatively, a paper consent can be obtained. The study team will access the latest consent form from REDCap, print it, and proceed with the consent discussion with family. Once the consent has been fully executed, a copy will be provided to the family and uploaded to REDCap.

After consent is obtained, measures will be completed by the parent in the REDCap (PIP, ITQOL or CHQ, RAND SF-36, PedsQL). Parents will be asked for 3 days/times when research staff can call them to complete the three 24 hour dietary phone recalls (24hr DR). Participants will be given a supplies for the 4 stool collections and be asked to collect the sample at home 1-7 days prior to each clinic visit (Week 0, 10, 14, 24), store in their home freezer, and return the sample at their study visit. Families will be scheduled for their first study visit in approximately 1 to 14 days.

6.2 Clinic Visit 1 (Week 0)

Participants will be given a full medical history and exam (including vital signs). Height and weight will both be taken in triplicate via calibrated equipment by a trained staff member. Participants taking inhaled or internasal steroids will complete a blood draw (morning cortisol). Participants who are not taking inhaled or intranasal steroids will not complete a blood draw during the Week 0 visit. If an abnormal morning cortisol value is measured, follow the redraw procedures under section 3.4 Primary Safety Endpoints. Participants will bring in a frozen stool sample. Subjects will remain on their current G or G/J tube feeding regimen as determined by their clinical feeding team. If patient is volume sensitive, the feeding team may intervene clinically by placing the subject on continuous feeds when indicated. Families will be encouraged to contact team members with questions or concerns at any time throughout the study period. Participants who complete the measures at pre-screening and complete Clinic Visit 1 will be randomized to an intervention by the study statistician. Participants will be asked measure the child's weight using a digital home weight scale. If the family does not have a digital weight scale, one will be provided to them.

6.3 Tele-Visit (Weeks 1, 3, 5, 7, 9)

Participants will complete a tele-visit with a member of the study team to discuss parent perception of changes in weight, feeding habits, progress, stress of parent/child, and illness. Participants will be asked to measure the child's weight using a digital home weight scale. Families will be encouraged to contact team members with questions or concerns at any time throughout the study period.

6.4 Clinic Visit 2 (Week 10)

Participants will return to clinic to complete vital signs and blood draw (morning cortisol). If an abnormal morning cortisol value is measured, follow the redraw procedures under section 3.4 Primary Safety Endpoints. Height and weight will both be taken in triplicate via calibrated equipment by a trained staff member. Participants will bring in a frozen stool sample. Patients will be given megestrol or placebo, but asked to wait to administer the 1st dose until lab value for morning cortisol are confirmed normal. Megestrol will be dosed at 6 mg/kg/d at weeks 10-11, at 4 mg/kg/d at week 12, at 2 mg/kg/d at week 13, and fully tapered at the end of week 13. Participants will be asked to complete the PIP, ITQOL or CHQ, RAND SF-36, PedsQL and schedule three 24 hr Dietary recall phone calls over the coming week. Five

CONFIDENTIAL

This material is strictly confidential and is intended solely for the guidance of clinical investigation. Do not disclose or use except as authorized in writing by the study sponsor

days after the clinic visit, parents will begin to taper G or G/J tube feedings by 10% each day until they are stopped altogether. Families will be encouraged to contact team members with questions or concerns at any time throughout the study period.

6.5 Tele-Visit (Week 11)

Participants will complete a tele-visit with a member of the study team to discuss the child's response to treatment, parent perception of changes in weight, feeding habits, progress, stress of parent/child, and illness. Participants will be asked to measure the child's weight using a digital home weight scale. Megestrol will be continued daily at the full dose. Parents will be asked about any major changes in their health, appetite, and medications. Families will be encouraged to contact team members with questions or concerns at any time throughout the study period.

6.6 Tele-Visit (Week 12)

Participants will complete a tele-visit with a member of the study team to discuss the child's response to treatment, parent perception of changes in weight, feeding habits, progress, stress of parent/child, and illness. Participants will be asked to measure the child's weight using a digital home weight scale. Megestrol will be continued daily at 4 mg/kg/d. Parents will be asked about any major changes in their health, appetite, and medications. Families will be encouraged to contact team members with questions or concerns at any time throughout the study period.

6.7 Tele-Visit (Week 13)

Participants will complete a tele-visit with a member of the study team to discuss the child's response to treatment, parent perception of changes in weight, feeding habits, progress, stress of parent/child, and illness. Participants will be asked to measure the child's weight using a digital home weight scale. Megestrol will be continued daily at 2 mg/kg/d. Parents will be asked about any major changes in their health, appetite, and medications. Families will be encouraged to contact team members with questions or concerns at any time throughout the study period.

6.8 Clinic Visit 3 (Week 14)

Participants will return to clinic to complete vital signs and blood draw (morning cortisol). The morning cortisol lab value must be taken at least 5 days after the final dose of study drug, so verify with the family when the last dose will be taken before scheduling the Week 14 visit. If an abnormal morning cortisol value is measured, follow the redraw procedures under section 3.4 Primary Safety Endpoints. Height and weight will both be taken in triplicate via calibrated equipment by a trained staff member. At the visit they will also complete the PIP, ITQOL or CHQ, RAND SF-36, PedsQL and schedule three 24 hr Dietary recall phone calls over the coming week. Participants will bring in a frozen stool sample. Tube feedings and megestrol will have ceased. Parents will be asked about any major changes in their health, appetite, and medications

6.9 Tele-Visit (Week 14)

Participants will complete a tele-visit with a member of the study team to discuss parent perception of changes in weight, feeding habits, progress, stress of parent/child, and illness. Participants will be asked

CONFIDENTIAL

This material is strictly confidential and is intended solely for the guidance of clinical investigation. Do not disclose or use except as authorized in writing by the study sponsor

to measure the child's weight using a digital home weight scale. Families will be encouraged to contact team members with questions or concerns at any time throughout the study period

6.10 Tele-Visits (Weeks 15, 17, 19, 21, 23)

Participants will complete a tele-visit with a member of the study team to discuss parent perception of changes in weight, feeding habits, progress, stress of parent/child, and illness. Participants will be asked to measure the child's weight using a digital home weight scale. Families will be encouraged to contact team members with questions or concerns at any time throughout the study period.

6.11 Clinic Visit 4 (Week 24)

Participants will return to clinic to complete vital signs and measures (PIP, ITQOL or CHQ, RAND SF-36, PedsQL) and schedule three 24 hr Dietary recall phone calls over the coming week. Participants will bring in a frozen stool sample. Families will be encouraged to contact team members with questions or concerns at any time throughout the study period.

At every clinic visit and tele-visit we will record and evaluate concomitant medications. Also, if any safety concerns are noted at any clinic or tele-visit, additional visits may occur. Should any clinical concerns be noted, appropriate medical/clinical treatments will also occur as necessary. If any serious adverse events occur (as outlined elsewhere), providers will be unblinded to the subject's group, the subject will be removed from the study and patients will receive all necessary treatment clinically.

7 Statistical Plan

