patients will be contacted weekly while taking the medication (via the Tele-visits described previously) for any negative gastrointestinal, behavioral, feeding, or other negative sequelae suspected to result from the medications. (If such patients are subjected to stress such as an infection or surgery, they may develop adrenal crisis. The patient suddenly becomes cyanotic and cold, blood pressure drops, and without immediate resuscitation the patient goes into shock). If any negative outcomes are identified they will be reported to our Data Safety and Monitoring Board and proper steps will be taken.

Under certain conditions children may removed from the study and treated clinically. The medical monitor and site PI will assess the case and determine if it is safe for the participant to continue.

Risk/benefit assessment:

Our previous work suggests that iKanEat is effective in moving children from tube to oral eating, and that amitriptyline does not improve the outcomes associated with the protocol. However, we do not know if the remaining medication (megestrol) improves the outcomes associated with iKanEat. As all medications have risks, it is necessary to test this remaining medication to determine if the risk is outweighed by the benefit the medication brings to the iKanEat protocol.

Data Safety Monitoring Board

For the current study we will have a Data Safety Monitoring Board that will review all subject safety data twice annually. DSMB will review protocol adherence, adverse events, unanticipated problems, voluntary and study team initiated withdrawals, etc. This team is available to the investigators at any time should an issue of safety arise, as was the DSMB for their previous study (HD068221). This board will be composed of [name], Professor of Pediatrics and [name], Professor, Rady Children's Hospital and UCSD. Twice annual conference calls will be held between the DSMB members and the investigation team to assure the best outcome for all subjects. Any serious adverse events will be reported immediately to the relevant institutional IRBs and to the DSMB.

Population(s) for Analysis. Our primary analysis will focus on a protocol-compliant population, but we will secondarily also analyses the all-treated population, as described below.

- All-randomized population: Any subject randomized into the study, regardless of whether they received study drug

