8.1 Definitions

Unanticipated Problems Involving Risk to Subjects or Others

For the current study, we will use CTCAE criteria, incorporating the additional considerations about pediatric effects and regarding hospitalization. Any incident, experience, or outcome that meets all of the following criteria:

- Unexpected in nature, severity, or frequency (i.e. not described in study-related documents such as the IRB-approved protocol or consent form, the investigators brochure, etc.)
- Related or possibly related to participation in the research (i.e. possibly related means there is a reasonable possibility that the incident experience, or outcome may have been caused by the procedures involved in the research)

CONFIDENTIAL

This material is strictly confidential and is intended solely for the guidance of clinical investigation. Do not disclose or use except as authorized in writing by the study sponsor

- Suggests that the research places subjects or others at greater risk of harm (including physical, psychological, economic, or social harm).

Adverse Event

An **adverse event** (AE) is any symptom, sign, illness or experience that develops or worsens in severity during the course of the study. Intercurrent illnesses or injuries should be regarded as adverse events. Abnormal results of diagnostic procedures are considered to be adverse events if the abnormality:

- results in study withdrawal
- is associated with a serious adverse event
- is associated with clinical signs or symptoms
- leads to additional treatment or to further diagnostic tests
- is considered by the investigator to be of clinical significance

Serious Adverse Event

Adverse events are classified as serious or non-serious. A **serious adverse event** is any AE that is:

- fatal
- life-threatening
- requires or prolongs hospital stay
- results in persistent or significant disability or incapacity
- a congenital anomaly or birth defect
- an important medical event

Important medical events are those that may not be immediately life threatening, but are clearly of major clinical significance. They may jeopardize the subject, and may require intervention to prevent one of the other serious outcomes noted above. For example, drug overdose or abuse, a seizure that did not result in in-patient hospitalization, or intensive treatment of bronchospasm in an emergency department would typically be considered serious.

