All adverse events that do not meet any of the criteria for serious should be regarded as **non-serious adverse events**.

Adverse Event Reporting Period

The study period during which adverse events must be reported is normally defined as the period from the initiation of any study procedures to the end of the study treatment follow-up. For this study, the study treatment follow-up is defined as 30 days following the last administration of study treatment.

Preexisting Condition

A preexisting condition is one that is present at the start of the study. A preexisting condition should be recorded as an adverse event if the frequency, intensity, or the character of the condition worsens during the study period.

General Physical Examination Findings

At screening, any clinically significant abnormality should be recorded as a preexisting condition. At the end of the study, any new clinically significant findings/abnormalities that meet the definition of an adverse event must also be recorded and documented as an adverse event.

Post-study Adverse Event

All unresolved adverse events should be followed by the investigator until the events are resolved, the subject is lost to follow-up, or the adverse event is otherwise explained. At the last scheduled visit, the investigator should instruct each subject to report any subsequent event(s) that the subject, or the subject's personal physician, believes might reasonably be related to participation in this study. The investigator should notify the study sponsor of any death or adverse event occurring at any time after a subject has

CONFIDENTIAL

This material is strictly confidential and is intended solely for the guidance of clinical investigation. Do not disclose or use except as authorized in writing by the study sponsor

discontinued or terminated study participation that may reasonably be related to this study. The sponsor should also be notified if the investigator should become aware of the development of cancer or of a congenital anomaly in a subsequently conceived offspring of a subject that has participated in this study.

Abnormal Laboratory Values

A clinical laboratory abnormality should be documented as an adverse event if any one of the following conditions is met:

- The laboratory abnormality is not otherwise refuted by a repeat test to confirm the abnormality
- The abnormality suggests a disease and/or organ toxicity

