- The abnormality is of a degree that requires active management; e.g. change of dose, discontinuation of the drug, more frequent follow-up assessments, further diagnostic investigation, etc.

Hospitalization, Prolonged Hospitalization or Surgery

For the current study, we will use CTCAE criteria, incorporating the additional considerations about pediatric effects and regarding hospitalization. Any adverse event that results in hospitalization or prolonged hospitalization should be documented and reported as a serious adverse event unless specifically instructed otherwise in this protocol. Any condition responsible for surgery should be documented as an adverse event if the condition meets the criteria for an adverse event.

Neither the condition, hospitalization, prolonged hospitalization, nor surgery are reported as an adverse event in the following circumstances:

- Hospitalization or prolonged hospitalization for diagnostic or elective surgical procedures for a preexisting condition. Surgery should **not** be reported as an outcome of an adverse event if the purpose of the surgery was elective or diagnostic and the outcome was uneventful.
- Hospitalization or prolonged hospitalization required to allow efficacy measurement for the study.
- Hospitalization or prolonged hospitalization for therapy of the target disease of the study, unless it is a worsening or increase in frequency of hospital admissions as judged by the clinical investigator.

Expected and Unexpected event criteria

Side effects of megestrol affect up to 5% of adults and older children. Those expected side effects include:

- Diarrhea
- Rash
- Gas
- High blood pressure
- Weakness
- Trouble sleeping
- Nausea
- Low levels of oxygen in the blood causing pall skin color and sleepiness
- Adrenal insufficiency (pale skin color, cold to the touch, weight loss, thirsty, dizzy or disoriented)
- Fever
- Stomach pain and discomfort
- Heartburn
- High levels of sugar in the blood, which can cause tiredness, blurry vision, increased thirst and hunger, and passing urine often.
- Headache
- Pain
- Vomiting
- Pneumonia
- Urinary Frequency

CONFIDENTIAL

This material is strictly confidential and is intended solely for the guidance of clinical investigation. Do not disclose or use except as authorized in writing by the study sponsor

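### Section 6.11 makes unblinding and removal automatic after any serious adverse event, even an unrelated one or one before the first dose

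*Combined protocol and SAP*

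**What the plan says.** The rule is in the closing paragraph of Section 6.11 (Clinic Visit 4): "If any serious adverse events occur (as outlined elsewhere), providers will be unblinded to the subject's group, the subject will be removed". The sentence makes clear that this means removal from the trial, with any needed treatment given as clinical care. Both consequences are mandatory. The parenthesis most naturally refers to the definitions in Section 8.1.

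Section 8.1 sets a wide trigger:

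- On adverse events: "Intercurrent illnesses or injuries should be regarded as adverse events".
- One criterion for seriousness is that the event "requires or prolongs hospital stay".
- The hospitalization paragraph repeats this: "Any adverse event that results in hospitalization or prolonged hospitalization should be documented and reported as a serious adverse event". Exceptions cover elective or diagnostic procedures, efficacy measurement and most stays for the target disease.
- Reporting covers "the period from the initiation of any study procedures to the end of the study treatment follow-up", so events count before any drug is given.

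Other sections are softer. The Safety text in Section 7 says "Under certain conditions children may removed from the study and treated clinically", and then "The medical monitor and site PI will assess the case and determine if it is safe for the participant to continue". Section 8.4 expects most unblinding to happen while a serious adverse event is being managed. It sets reporting times but no criterion for breaking the code.

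**The concern.** Read literally, 6.11 requires a code break and a removal for events that give no reason for either. The clearest case is a randomized child admitted in week 3 with an unrelated infection. No study drug has been taken, so the assignment cannot guide treatment, yet the providers must be told it and the child must leave the study.

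Three things are at stake. The blind is broken without clinical benefit. A child loses a place in the 24-week program in a trial of only 60 to 72 children described as medically complex. And a removed child would probably drop out of the protocol-compliant population used for the primary analysis, although that definition leaves its processing requirement unexplained. Whether that population should be primary is a separate question and is not argued here.

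The week 24 outcome need not be lost. Section 4.4.1 uses the word removed under its withdrawal heading, and 4.4.2 then asks withdrawn children for further assessments, so the diet recalls are probably still requested.

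**Working it through.** **Is the 6.11 rule limited anywhere?** The plan states no figure on this point, so the first check is textual.

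| Place | What it governs | Does it limit 6.11? |
|---|---|---|
| 8.1, definitions | Seriousness; some hospital stays exempt | No test of relatedness, exposure or need |
| 8.4 | Times for reporting an unblinding | No criterion for when to unblind |
| 4.4.1 | Weight-loss triggers, with case review | Serious adverse events not listed |
| Section 7, Safety | Possible removal after assessment | General; mentions neither serious adverse events nor unblinding |
| 8.5 | Stopping rules for the whole study | Requires relatedness, but only for stopping the study |
| 3.4 | Two abnormal morning cortisol values | Pause, endocrinology input, then resume or remove |

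No section narrows the rule. The ordering is also odd. Under 3.4, a child with confirmed abnormal cortisol, the signal for the drug's main known toxicity, may resume. Under 6.11, a child with an unrelated admission may not.

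**How much of the protocol precedes exposure?** Randomization follows Clinic Visit 1 at week 0 (6.2). The first dose waits for a normal week 10 cortisol result (6.4). Dosing covers weeks 10 to 13 (5.2). Section 6.11 is not restricted to the adverse event reporting window, so the whole 24 weeks is used:

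- Total: 24 × 7 = 168 days.
- Before drug: 10 × 7 = 70 days; 70/168 = 41.7%.
- On drug: 4 × 7 = 28 days; 28/168 = 16.7%.
- After drug: 168 − 70 − 28 = 70 days; 70/168 = 41.7%.

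These are shares of calendar time, not of events. They are approximate: waiting for the cortisol result, or a pause in weeks 1 to 9, lengthens the first part.

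**Illustrative counts.** The documents give no serious adverse event rate. Assume a 24-week risk *p* per child and a constant hazard.

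- Expected children with an event = N × p.
- Expected children with an event before dosing = N × [1 − (1 − p)^(70/168)].

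| p (assumed) | N = 72: any event | N = 72: before dosing | N = 60: any event | N = 60: before dosing |
|---|---|---|---|---|
| 5% | 3.6 | 1.5 | 3 | 1.3 |
| 10% | 7.2 | 3.1 | 6 | 2.6 |
| 20% | 14.4 | 6.4 | 12 | 5.3 |

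For example, with p = 10% and N = 72: 72 × (1 − 0.90^0.4167) = 72 × 0.0430 = 3.1. If events cluster in the weaning weeks, the pre-dose counts are lower.

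**The case against.** The strongest reply is that 6.11 is one loosely worded sentence at the end of a visit section, and that the rest of the protocol handles illness case by case. Section 8.1 allows a pause for medical concerns in weeks 1 to 9 that disrupt feeding without meeting withdrawal criteria. Section 5.4 lets the medical monitor suspend and later restart study drug around a steroid course. Section 3.3 keeps a child in the study when acute illness forces a temporary return to tube feeding. Section 8.3 asks the event narrative to say whether treatment was stopped, which would be largely redundant during dosing if every serious adverse event forced removal. All this is correct and shows that 6.11 is out of line with its surroundings. None of it overrides 6.11. The week 1 to 9 pause applies only short of the withdrawal criteria, and the text does not settle whether 6.11 is itself such a criterion. A site that follows 6.11 removes children needlessly; a site that does not follow it deviates from the protocol.

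The second reply is that harm is not shown. The counts rest on assumed rates, the rule unblinds providers while the Kansas team conducts the recalls, and recruiting 72 to retain 60 leaves 12 places for losses. The size is indeed unknown, and no bias in the endpoint has been demonstrated. The 5% and 10% scenarios (3.6 and 7.2 children) fit within 12 places and the 20% scenario (14.4) does not, but those places must also absorb every other kind of loss.

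The third reply is clinical. The Safety text warns: "If such patients are subjected to stress such as an infection or surgery, they may develop adrenal crisis". Clinicians may want to know exposure before adrenal insufficiency is suspected. This stands for the periods during and after dosing. It supports ready unblinding on clinical need; it does not support automatic unblinding, and it has no force before the first dose.

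**Conclusion.** The concern holds. Section 6.11 is unconditional, its trigger is defined by seriousness alone, and no other section limits it. For about 70 of 168 days the required unblinding cannot help care, because no drug has been taken. The reading of the text is secure. The effect on the trial is not known: the counts depend on assumed risks of 5% to 20% and a constant hazard, the loss from the primary analysis set is probable rather than stated, and the week 24 recalls are probably retained. The change should be made because the rule does worse than case review whenever it is followed as written, and correcting it is cheap.

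**What to change.** Reword 6.11 and align 8.4 with it, so that after a serious adverse event:

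1. The medical monitor and site investigator decide case by case whether study drug and participation continue.
2. The code is broken only when clinical management needs it, for example for suspected adrenal insufficiency, or for serious infection or surgery, during or after dosing. The treating clinician stays free to unblind at once when care requires it.
3. A child who stops is still asked for the week 14 and week 24 recalls. Section 4.4.2 should name removed as well as withdrawn children.

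The cost is wording in three sections and a case review for each serious adverse event. Section 8.6 already has the medical monitor review every reported adverse event, so no visit or procedure is added. To avoid delay in an emergency, the text should say that urgent unblinding does not wait for that review.
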